#### 9.3. Relationship to Investigational Drug Treatment

An Investigator's causality assessment is the determination of whether a reasonable possibility exists that the investigational drug caused or contributed to an AE. This assessment must be provided for all AEs (serious and non-serious).

The Sponsor's determination of attribution will be used for reporting to the appropriate health authorities. The relation of an AE to study participation will be determined using the descriptors and definitions provided in Table 4.

#### Table 4: Attribution of Adverse Events

Not Related	The AE is clearly/most probably caused by other etiologies such as participant's underlying condition, therapeutic intervention or concomitant therapy, or the delay between administration and the onset of the AE is incompatible with a causal relation, or the AE started before administration (screening phase). Therefore, there is not a reasonable possibility that the AE was caused by the investigational drug.
Possible Related	An adverse event that has a timely relationship to the administration of the investigational drug/study procedure, follows no known pattern of response, but a potential alternative cause does not exist.
Probably Related	An adverse event that has a timely relationship to the administration of the investigational drug/study procedure and follows a known pattern of response, but for which a potential alternative cause may be present.
Definitely Related:	An adverse event that has a timely relationship to the administration of the investigational drug and follows a known pattern of response for which no alternative cause is present.

#### 9.4. Collecting and Recording Adverse Events

#### 9.4.1. Period of Collection

All AEs will be collected from the completion of informed consent through Visit 4. All AEs and SAEs should be treated as medically appropriate. AEs that occur after at least one dose of study medication has been administered will be considered treatment-emergent AEs.

#### 9.4.2. Methods of Collection

Adverse events may be collected as follows:

- Observing the subject
- Questioning the subject in an unbiased and non-leading manner
- Receiving an unsolicited complaint from the subject or parent/guardian

An abnormal value or result from a clinical or laboratory evaluation (e.g., physical examination, laboratory assessment, or ECG) can also indicate an AE if it is determined by the Investigator to be clinically significant. If this is the case, it must be recorded in the source document and as an AE on the appropriate AE form(s). The evaluation that produced the value or result should be repeated until that value or result returns to normal or is stabilized and the participant's safety is not at risk.

#### 9.4.3. Recording Method

#### 9.4.3.1. Adverse Events

All AEs occurring during this clinical study will be recorded by the Investigator on the appropriate CRF in precise medical terms, along with the date and time of onset and the date and time of resolution. To avoid vague, ambiguous, or colloquial expressions, the AE should be recorded in standard medical terminology rather than the subject's own words. Whenever possible, the Investigator should combine signs and symptoms into a single term that constitutes a single diagnosis. Each AE is to be evaluated for duration, severity, seriousness, and relatedness to the study medication. The severity of the AE and its relationship to the study medication will be assessed by the Investigator.

The Investigator will treat participants experiencing AEs appropriately and observe them at suitable intervals until their symptoms resolve or their status stabilizes. If any medication is administered in response to the AE, this medication should be noted on the concomitant medication CRF as a concomitant medication administered. The action taken and the outcome must also be recorded. Adverse events will be followed until resolution or stabilization or until 30 days after a participant terminates from the study, whichever comes first. The terms of AE resolution (i.e., not recovered/not resolved, recovering/resolving, recovered/resolved, recovered/resolved with sequelae, fatal, unknown) should also be recorded.

#### 9.4.3.2. Serious Adverse Events

Serious adverse events will be recorded on the AE CRF and on the SAE Report Form Provided by the sponsor as described in Section 9.4.3.1, and health authorities will be notified as outlined in Section 9.5.2.

#### 9.5. Reporting Adverse Events

#### 9.5.1. Reporting SAEs to the Sponsor

The following process for reporting an SAE ensures compliance with 21 CFR 312 and ICH guidelines. After learning that a participant has experienced an SAE, the Investigator or designee is responsible for reporting the SAE to the sponsor, regardless of relationship or expectedness, within 24 hours of becoming aware of the event. The initial SAE report should include as much information as possible, but at a minimum must include the following:

- Name of the reporter
- Subject identification
- Study drug
- Serious AE term
- Date of onset
- Relationship to study drug
- Reason why the event is serious

Supplemental CRF pages should be current at the time of SAE reporting: medical history, concomitant medications, demographics, study drug administration, and death (as applicable).

Unavailability of certain event details should not delay submission of the known information. As additional details become available, the SAE CRF should be updated and re-submitted. Every time the SAE CRF is submitted, it should be signed by the Investigator or sub-investigator.

The following Sponsor Representative is to be contacted immediately after the occurrence of an SAE:

#### 9.5.2. Reporting SAEs to Health Authorities

The Sponsor or Sponsor designee will report Investigational New Drug (IND) Safety Reports to the FDA and Investigators in accordance with the FDA regulations detailed in the 21 CFR 312.32.

#### 9.5.3. Reporting SAEs to the Central IRB(s)

It is the responsibility of the Sponsor or Sponsor designee to promptly notify their respective IRB(s) of IND Safety reports or other matters involving risk to subjects as mandated by the IRB(s).

#### 9.5.4. Reporting Pregnancy

During the study, all subjects should be instructed to contact the Investigator immediately if they suspect they might be pregnant (e.g., missed or late menstrual period). If pregnancy is confirmed, the subject will be withdrawn from the study and followed until the pregnancy comes to term.

The Investigator is responsible for reporting all available pregnancy information on the pregnancy CRF within 24 hours of becoming aware of the event, although pregnancy itself is not an SAE. The Investigator should counsel the participant and discuss the risks of continuing with the pregnancy and the possible effects on the fetus. The subject should be referred to an obstetrician/gynecologist experienced in reproductive toxicity for further evaluation and counseling. Monitoring of the participant should continue until the conclusion of the pregnancy. Follow-up information detailing the outcome of the pregnancy should be reported as it becomes available.

Any pregnancy complication or premature terminations including miscarriage, spontaneous abortion, or elective termination of a pregnancy for medical reasons will be reported as an SAE, as described in Section 9.5.1. Should the pregnancy result in a congenital abnormality or birth defect, a separate SAE

report must be submitted. Furthermore, all neonatal deaths that occur within 30 days of the birth should be reported as SAEs, without regard to causality. In addition, any infant death that occurs after the 30-day reporting period that the Investigator suspects is related to the in-utero exposure to the study treatment should also be reported.

# **10. STATISTICS**

#### **10.1.** Power and Sample Size Determination

The primary efficacy outcome is change from pre-dose in the model-adjusted SKAMP-Combined score at 30 minutes hours post-dose as measured during the laboratory school days (Visits 3 and 4). Assuming an effect size of 1.00 between Dyanavel XR and placebo and approximately 15 subjects randomized to double-blind treatment, this study will have 90% power at the level of alpha = 0.05 (2-sided) to detect a treatment effect. To allow for an estimated 15% potential drop-out rate, this study plans to enroll approximately 18 subjects.

The assumed effect size is based on differences measured between active and placebo in previous laboratory school studies conducted with similar drug formulations at the earliest measured timepoint and reducing that by 20%.

A detailed statistical analysis plan (SAP) will be written and finalized prior to unblinding of the data.

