# **1. INTRODUCTION**

Amphetamine has been a well-established therapeutic agent for the treatment of Attention Hyperactivity Disorder (ADHD) for decades. Since the original amphetamine approval, various dosage forms have been approved for use:

- immediate release (IR) dosage forms, oral solution and tablets.
- extended release (ER) dosage forms, capsules, and tablets with various release technologies

Dyanavel XR is an extended-release oral suspension (EROS) that contains 2.5mg/mL amphetamine base. Drug-resin complexation is formed with the amphetamine and Sodium Polystyrene Sulfonate USP, an ion exchange resin. The extended release feature of the product is achieved by coating some drug/resin complexes with an extended-release coating. Dyanavel XR contains approximately a 3:1 ratio of damphetamine compared to l-amphetamine.

The efficacy of Dyanavel XR in the treatment of ADHD in children ages 6-12 has been established in a Phase 3 placebo-controlled laboratory classroom study: TRI102-ADD-001. ADHD symptoms in children on an individually optimized dose of amphetamine (range 10-20 mg/day) were significantly lower compared to symptoms experienced by children treated with placebo. Symptom control was demonstrated 1 hour after dosing and efficacy was observed through 13 hours beyond dosing. The effect size in this study was in line with effect sizes demonstrated for other psychostimulants tested in a similar study design. The adverse events in this study were expected for amphetamine treatment with respect for type of adverse event, frequency and severity.

Study TRI102-PPK-200 was conducted in children ages 6 to 12 years old with ADHD to evaluate the single-dose (10 mg) pharmacokinetics of orally administered Dyanavel XR. Following a single 10 mg oral dose of Dyanavel XR in 12 pediatric subjects under fasting conditions, d-amphetamine and l-amphetamine peak plasma concentrations occurred at a median time of 3.9 and 4.5 hours after dosing, respectively. The mean plasma terminal elimination half-life of d-amphetamine was 10.43 ( $\pm$  2.01 h) hours and the mean plasma terminal half-life for l-amphetamine was 12.14 ( $\pm$  3.15 h) hours.

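### Does the stated 90% power fail to follow from an effect size of 1.00 and 15 children?

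*Protocol*

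**What the plan says.** Protocol Section 10.1 gives these planning inputs:

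- Effect and number: "Assuming an effect size of 1.00 between Dyanavel XR and placebo and approximately 15 subjects randomized to double-blind treatment".
- Claim: "this study will have 90% power at the level of alpha = 0.05 (2-sided").
- Enrolment: "To allow for an estimated 15% potential drop-out rate, this study plans to enroll approximately 18 subjects".
- Source of the effect: "based on differences measured between active and placebo in previous laboratory school studies conducted with similar drug formulations at the earliest measured timepoint", after which the same sentence takes off a further 20%. The 1.00 is thus already a discounted figure, from about 1.00/0.80 = 1.25.

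Section 3.1 describes a two-treatment, two-sequence crossover, and Section 8 randomises 1:1 to sequence. Section 10.2 admits a child to the ITT set only with a post-dose primary assessment at both Visits 3 and 4. Section 10.3.2.1 uses a mixed-effects repeated-measures model with a two-sided 5% test. The treatment comparison is therefore essentially within-child.

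Section 10.1 does not name the standardising SD, a within-child correlation or a power formula.

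**The concern.** The natural check is to put 1.00, 15 and 0.05 into the paired or crossover power formula. The answer is about 95%, not 90%. A reader may then suspect that 1.00 is a conventional between-child effect size. The Introduction could encourage this, since it reports symptoms on active treatment as "significantly lower compared to symptoms experienced by children treated with placebo". On that reading the power rests on a correlation that the protocol does not give, and it can fall well below 90%.

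Two further points seem to add to the doubt. The effect comes from the first measured time in earlier studies, and the only early time the Introduction reports is one hour ("Symptom control was demonstrated 1 hour after dosing and efficacy was observed through 13 hours beyond dosing"), whereas this trial tests 30 minutes. And 18 enrolled less 15% appears to give 15 randomised, which leaves nothing for children lost after randomisation.

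At stake is the only justification for the size of a small single-site paediatric trial. If 1.00 were a between-child effect and the correlation were zero, 90% power would need 24 children rather than 15.

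**Working it through.** **Inputs.** Effect size 1.00, n = 15, two-sided alpha 0.05, stated power 90%, dropout 15% (all Section 10.1); 2x2 crossover (Sections 3.1 and 8). The within-child correlation rho is not given, so I assume a range of 0 to 0.6. It is the correlation between a child's two change-from-pre-dose scores.

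**Formula.** Let dz be the mean within-child difference divided by the SD of within-child differences. Power is the noncentral t probability beyond the 5% critical values, with noncentrality dz x sqrt(n). Degrees of freedom are n - 2 = 13 (crossover with a period effect) or n - 1 = 14 (paired t-test).

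**Reading 1: 1.00 is a within-child effect.** dz = 1.00 and the noncentrality is sqrt(15) = 3.873.

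- n = 15: 94.7% (13 df) or 94.9% (14 df).
- n = 13: 90.6% (11 df) or 91.1% (12 df). This is the smallest n that reaches 90%; n = 12 gives 87.6% or 88.3%.

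The stated 90% is then on the safe side. Fifteen children less 15% is 12.75, and that value in the same formula (n - 2 df) gives 89.9%. This is one possible route to the printed figure, though the text does not say it was used.

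**Reading 2: 1.00 is a between-child effect.** With equal SDs under both treatments, dz = 1/sqrt(2(1 - rho)). For n = 15 and 13 df:

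| rho | dz | Noncentrality | Power |
|---|---|---|---|
| 0 | 0.707 | 2.739 | 72% |
| 0.2 | 0.791 | 3.062 | 81% |
| 0.3 | 0.845 | 3.273 | 86% |
| 0.39 | 0.905 | 3.506 | 90% |
| 0.5 | 1.000 | 3.873 | 95% |
| 0.6 | 1.118 | 4.330 | 98% |

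Conversely, 90% power at n = 15 (13 df) needs dz = 0.906, so rho = 1 - 1/(2 x 0.906^2) = 0.391. With 14 df it is 0.384. The stated 90% is exact near 0.39, optimistic below and conservative above.

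**Two-sample readings.** Fifteen per arm would give 75% and 15 in total 43%. Neither applies, because each child receives both treatments.

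**Dropout.** 15/0.85 = 17.6, rounded up to 18, as printed.

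**Loss after randomisation.** With 13 completers, power is about 91% if dz = 1.00 and 84% if dz = 0.906, the value that gives exactly 90% at 15. Randomisation is at Visit 2, Visit 3 is the next day and Visit 4 the following weekend (Section 5.3.1.4), so there is little time for such losses.

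**A smaller effect at 30 minutes.** With n = 15 and 13 df, dz = 0.8 gives 82% and dz = 0.7 gives 71%. These values assume cuts of 20% and 30% on top of the 20% already taken. Section 10.1 names no source study, and the Introduction does not say that one hour was the first measurement in the study it describes. That 30 minutes precedes the source timepoint is therefore not established.

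**The case for a change.** The strongest case for acting is that an effect size in a crossover is undefined until its SD is named. The protocol itself prints the effect, the number and the power as its justification, so this is not something left to the SAP. No direct use of the printed inputs alone comes within two points of 90%: the within-child reading gives about 95%, and every route to 90% needs something unstated. One paragraph in Section 10.1 would settle it.

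Much of this stands. The SD and the correlation are missing, and the 90% cannot be checked. A low correlation cannot be excluded either: a change score removes much of what is stable about a child, so two change scores need not be strongly correlated.

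The step from unverifiable to wrong does not stand. The Introduction's comparison with placebo-treated children is a narrative result. It names no SD, does not say whether that study was parallel or crossover, and is not tied to the 1.00. The 72% figure needs a correlation of exactly zero, and the same calculation gives 95% to 98% at 0.5 to 0.6. Nor would a null result become uninterpretable, because it would be read from the estimate and its confidence interval rather than from the planned power.

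Rewriting the paragraph from the documents alone could also mislead. Declaring 1.00 a within-child effect and printing 95% would replace an unverified figure with a higher one that has no better support.

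**Conclusion.** No change to the plan follows. Section 10.1 omits the SD and any correlation behind its effect size, but the stated 90% lies inside the range the inputs allow: about 95% with 15 children on the within-child reading, and 72% to 98% on the between-child reading for correlations from 0 to 0.6, with 90% at about 0.39. This is a gap in reporting, not an arithmetic error.

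The sample size would look short only if 1.00 is a between-child effect and the correlation is clearly below 0.39, and the documents support neither assumption over its alternative. The primary test, its alpha and the analysis set do not depend on the planning SD. If the sponsor still has the original calculation, recording the SD and correlation used would help a reader, but it would alter neither enrolment nor analysis. The power figures assume a noncentral t for the within-child contrast and, on the between-child reading, equal SDs under the two treatments.

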Study 2014-3401 was conducted in 29 healthy adult subjects in a crossover study under fasting conditions, following a single, 18.8 mg oral dose of DYANAVEL XR. d-amphetamine and l-amphetamine, the median (range) time to peak plasma concentrations ( $T_{max}$ ) were 4.0 (2 – 7) hours after dosing and peak concentration ( $C_{max}$ ) were 102% and 106%, respectively of the  $C_{max}$  of immediate-release (IR) mixed amphetamine salts tablets. The relative bioavailability of DYANAVEL XR compared to an equal dose of mixed amphetamine salts IR tablets is 106% of d-amphetamine and 111% for l-amphetamine.

See the Dyanavel XR Package Insert for further information.

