# **2. OBJECTIVES**

#### 2.1. Efficacy Objective

To demonstrate that Dyanavel XR has an onset of action as early as 30 minutes post-dose as determined by change from pre-dose in SKAMP-Combined scores at 30 minutes post-dose during the laboratory school days (Visits 3 & 4), relative to placebo.

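### Does sizing a 30-minute test on an effect from earlier studies' earliest timepoint leave 15 children with well under 90% power?

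*Protocol*

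**What the plan says.** Section 10.1 (Power and Sample Size Determination) makes a conditional statement: with an "effect size of 1.00 between Dyanavel XR and placebo and approximately 15 subjects randomized to double-blind treatment, this study will have 90% power" at two-sided alpha 0.05. Enrolment is set at about 18 to allow for 15% drop-out. The effect size comes from "previous laboratory school studies conducted with similar drug formulations at the earliest measured timepoint and reducing that by 20" per cent. The section does not name those studies, their earliest timepoint in minutes or the effect before the cut.

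The objective in Section 2.1 is to show that the product "has an onset of action as early as 30 minutes post-dose".

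The Introduction says of the earlier laboratory classroom study of this product: "Symptom control was demonstrated 1 hour after dosing and efficacy was observed through 13 hours beyond dosing". For the single-dose study in children it says that "d-amphetamine and l-amphetamine peak plasma concentrations occurred at a median time of 3.9 and 4.5 hours after dosing, respectively", with a d-amphetamine half-life of 10.43 h. In adults the median (range) peak times "were 4.0 (2 – 7) hours after dosing". It gives no concentration at 30 minutes or 1 hour and no relation between concentration and effect.

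**The concern.** The primary test is at 30 minutes, so the power statement needs the drug–placebo difference at 30 minutes. The protocol reports no effect for this product before 1 hour, and plasma levels peak at about 4 hours. A reader can therefore suspect that the source effect was measured at 1 hour, while the drug effect was still rising. The 20% cut would then assume that four-fifths of the 1-hour effect is already present at 30 minutes, which is close to what the trial sets out to learn.

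A simple pharmacokinetic calculation seems to support the suspicion, because it puts the 30-minute level at 59% of the 1-hour level. If effect followed level, a real onset would be missed in about one trial in four to one in three, and a non-significant result could be misread as no onset at 30 minutes.

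**Working it through.** **Reproducing the plan's figure.** The inputs, all from Section 10.1, are effect size 1.00, n = 15, two-sided alpha 0.05, power 90% and drop-out 15%. Section 3.1 describes a two-sequence crossover, so the comparison is within child. Power comes from the noncentral t distribution with noncentrality d√n and n − 1 degrees of freedom.

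- If 1.00 is the mean difference over the SD of within-child differences, the noncentrality is 1.00 × √15 = 3.87 and power is 94.9%. The smallest n giving 90% is 13 (91.1%).
- If 1.00 is on the between-child SD, then d = 1/√(2(1 − ρ)), where ρ is the between-day correlation. Power with 15 is 90% at d = 0.90, that is ρ = 1 − 1/(2 × 0.901²) ≈ 0.38.
- Drop-out: 15/0.85 = 17.6, rounded up to 18.

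The 90% is therefore either exact or conservative, depending on the scale.

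**Where 67–76% comes from.** The source effect before the cut is 1.00/0.80 = 1.25. Take a one-compartment model with one first-order absorption rate:

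- Peak time 3.9 h and half-life 10.43 h give ke = ln 2/10.43 = 0.0665/h.
- Solving ln(ka/ke)/(ka − ke) = 3.9 gives ka = 0.652/h.
- C(t) is proportional to exp(−ke·t) − exp(−ka·t), so C(0.5 h)/C(1 h) = 0.592.
- The effect is then 1.25 × 0.592 = 0.74. Power with 15 is 76% on the paired scale and 67% on the scale where the stated 90% is exact.

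This arithmetic is correct. What matters is which of its inputs the protocol supplies.

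**Relaxing one assumption at a time** (n = 15; share is the 30-minute effect as a fraction of 1.25):

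| Case | Share | Power, scale where 90% is exact | Power, paired |
|---|---|---|---|
| 1-hour source, one absorption phase, effect proportional to level | 0.59 | 67% | 76% |
| Same, adult peak-time range 7 h to 2 h | 0.54–0.72 | 59–83% | 68–90% |
| 1-hour source, fast plus slow absorption | 0.62–0.79 | 71–89% | 80–94% |
| 45-minute source, one absorption phase | 0.73 | 84% | 90% |
| 1-hour source, saturating effect, half-maximal at the 1-hour level | 0.74 | 85% | 92% |
| The plan's own 20% cut | 0.80 | 90% | 95% |
| 30-minute source, no further loss | 1.00 | 98% | 99% |

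The fast-plus-slow row keeps the peak at 3.9 h and the half-life at 10.43 h. A fraction of 20–40% of the dose is absorbed at 1.5–4 per hour, and the slow rate is solved to hold the peak time. The fraction and fast rate are assumptions, because the protocol gives neither. A two-part form is reasonable because the Introduction says that only some of the drug–resin complexes carry the extended-release coating. With a 45-minute source the same fits give a share of 0.74–0.86, which partly exceeds 0.80.

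The reported peak time and half-life therefore do not fix the 30-minute share. The same two numbers are compatible with 0.59 and with 0.79 against a 1-hour source, before any question about the source time or the shape of the concentration–effect relation.

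**The source time.** Section 10.1 speaks of several earlier studies of similar formulations. It does not say that the 1-hour study in the Introduction was among them. The Introduction says that control was shown at 1 hour, not that 1 hour was the first time measured. Doses differ too: the pediatric pharmacokinetic figures are from 10 mg, the earlier classroom study used 10–20 mg/day, and the double-blind days here use 15, 17.5 or 20 mg. Even if that study were the source, a fixed share of its effect would not carry over directly.

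**The case for a change.** The strongest argument for the concern is that an onset trial should not leave its main unknown unsupported. The share of the effect present at 30 minutes is what the trial studies, yet Section 10.1 sets it through a flat 20% cut with no reason given. The protocol itself fixes the number of children, so a later analysis plan cannot repair a poor choice. On the scale where 90% is exact there is no margin: any share of the 1.25 below 80% brings power below 90%. In the one-absorption-phase model with a 1-hour source, no peak time within the reported 2–7 h range reaches 80%.

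Part of this stands. Section 10.1 would be easier to judge if it gave the source timepoint, the effect before the cut and the reason for 20%. The absence of margin on that scale is also true, but it holds for any sample size computed to give exactly 90%.

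The step from there to lost power does not stand. It needs a 1-hour source, one absorption phase and proportionality all to hold, and the protocol states none of them. The plan has also made some allowance already: it starts from the earliest available timepoint, not the peak effect, and then reduces it.

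**Conclusion.** The concern does not hold. Section 10.1 states power for an assumed effect of 1.00, and its figures follow from that assumption: 90–95% with 15 children, depending on the scale of the effect size, and 18 enrolled at 15% drop-out.

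The 67–76% is a sensitivity result under one set of unstated assumptions. Across the cases examined, power runs from 59% to 99%, and the fact that would decide among them, the source studies' earliest timepoint, is not in the protocol. A larger enrolment (26 to 31 children at a 59% share) or a lower stated power would rest wholly on that one model, so the document gives no ground to require either.

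What remains is an incomplete account of where the effect size came from. That is missing detail and does not show any stated figure to be wrong. The conclusion would change if the source time proved to be 1 hour or later and there were evidence that clearly less than 80% of that effect is present at 30 minutes.
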